## 6. DRUG FORMULATION AND ADMINISTRATION

### 6.1 Idelalisib

#### 6.1.1 Idelalisib Formulation

Idelalisib is provided as plain-faced or debossed, modified oval tablets. The 100-mg tablets are orange film-coated and the 150-mg tablets are pink film-coated. The debossed 100-mg tablets have "GSI" on one side and "100" on the other. The 150-mg tablets have "GSI" on one side and "150" on the other.

#### 6.1.2 Idelalisib Package, Storage and Handling

Idelalisib tablets are packaged in white, high-density polyethylene bottles with a polyester fiber coil and are closed by a polypropylene, child resistant induction-sealed cap. Bottles contain 60 tablets.

Measures that minimize drug contact with the body should always be considered during handling, preparation and disposal procedures. Any unused drug should be disposed of in accordance with local requirements.

Idelalisib tablets should be stored at a controlled room temperature between 20-30°C (68-86°F), with excursions permitted from 15°C (59°F) to 30°C (86°F). Brief excursion (less than 1 week) to temperatures as low as -10°C or as high as 40°C will not adversely affect the drug.

#### 6.1.3 Idelalisib Availability

Idelalisib is commercially available, but will be supplied free-of-charge from Gilead Sciences, Inc. Drug will be shipped to BMC by Gilead Sciences, Inc., with standard commercial labeling. As study visits are every three months, a three month supply of Idelalisib will be provided at each visit.

#### 6.1.4 Idelalisib Administration

Idelalisib should be self-administered daily by the participant and should be taken at approximately the same time each day. Idelalisib should be administered orally twice daily with 8 ounces (approximately 240 mL) of water (avoid GRAPEFRUIT JUICE due to CYP450 3A4 inhibition). The tablets should be swallowed intact and participants should not attempt to dissolve tablets in water. If a dose is missed, it can be taken up to 6 hours after the scheduled time with a return to the normal schedule the following day. If it has been greater than 6 hours, the dose should not be taken and the participant should take the next dose at the scheduled time the next day. The missed dose will not be made up and must be returned to the site at the next scheduled visit.

Dietary habits around the time of idelalisib intake should be as consistent as possible throughout the study. If the pills are vomited this should be noted on the diary, but a replacement dose should not be taken that day. A study diary will be used to aid with study drug administration compliance.

At each study visit, enough idelalisib will be dispensed until the next cycle. For visits occurring monthly, one cycle worth of pills will be dispensed. For visits occurring every 3 months, three cycles' worth of pills will be dispensed.

#### 6.1.5 Idelalisib Accountability

The investigator, or a responsible party designated by the investigator, must maintain a careful record of the inventory and disposition of the agent (investigational or free of charge) using the NCI Drug Accountability Record or another comparable drug accountability form. (See the CTEP website at <http://ctep.cancer.gov/protocolDevelopment> for the "Policy and Guidelines for Accountability and Storage of Investigational Agents" or to obtain a copy of the drug accountability form.)

**6.1.6 Idelalisib Destruction and Return**

Unused idelalisib tablets will be returned by the participant, collected and counted at each study visit, and will be destroyed per institutional policy. Destruction will be documented in the Drug Accountability Record Form.

**6.2 Bactrim DS****6.2.1 How Supplied**

BACTRIM™ DS (double strength) is commercially available as TABLETS (white, oval shaped, scored) containing 160 mg trimethoprim and 800 mg sulfamethoxazole – bottles of 100 (NDC 49708-146-01). Imprint on tablets (debossed): (front) BACTRIM DS. Please refer to the agent's package insert for additional information.

**6.2.2 Storage and Handling**

Store at 20° to 25°C (68° to 77°F). DISPENSE IN TIGHT, LIGHT-RESISTANT CONTAINER

**6.2.3 Toxicity**

- Hematologic: Agranulocytosis, aplastic anemia, thrombocytopenia, leukopenia, neutropenia, hemolytic anemia, megaloblastic anemia, hypoprothrombinemia, methemoglobinemia, eosinophilia.
- Allergic Reactions: Stevens-Johnson syndrome, toxic epidermal necrolysis, anaphylaxis, allergic myocarditis, erythema multiforme, exfoliative dermatitis, angioedema, drug fever, chills, Henoch-Schoenlein purpura, serum sickness-like syndrome, generalized allergic reactions, generalized skin eruptions, photosensitivity, conjunctival and scleral injection, pruritus, urticaria and rash. In addition, periarteritis nodosa and systemic lupus erythematosus have been reported.
- Gastrointestinal: Hepatitis (including cholestatic jaundice and hepatic necrosis), elevation of serum transaminase and bilirubin, pseudomembranous enterocolitis, pancreatitis, stomatitis, glossitis, nausea, emesis, abdominal pain, diarrhea, anorexia.
- Genitourinary: Renal failure, interstitial nephritis, BUN and serum creatinine elevation, toxic nephrosis with oliguria and anuria, crystalluria and nephrotoxicity in association with cyclosporine.
- Metabolic and Nutritional: Hyperkalemia, hyponatremia.
- Neurologic: Aseptic meningitis, convulsions, peripheral neuritis, ataxia, vertigo, tinnitus, headache.
- Psychiatric: Hallucinations, depression, apathy, nervousness.
- Endocrine: The sulfonamides bear certain chemical similarities to some goitrogens, diuretics (acetazolamide and the thiazides) and oral hypoglycemic agents. Cross-sensitivity may exist with these agents. Diuresis and hypoglycemia have occurred rarely in patients receiving sulfonamides.
- Musculoskeletal: Arthralgia and myalgia. Isolated cases of rhabdomyolysis have been reported with BACTRIM, mainly in AIDS patients.
- Respiratory: Cough, shortness of breath and pulmonary infiltrates.
- Miscellaneous: Weakness, fatigue, insomnia.

**6.2.4 Administration**

BACTRIM DS should be self-administered by the participant every Monday, Wednesday and Friday while taking idelalisib. Patients should be instructed to maintain an adequate fluid intake in order to prevent crystalluria and stone formation.

At each study visit, compliance will be assessed.

## 7.0 STUDY CALENDAR

	At enrollment	Every 2 weeks for 3-6 months after starting Idelalisib 	One and two months after starting Idelalisib 	Monthly while taking Idelalisib	Every three Months 	End of Study Treatment Visit 
PHYSICAL						
History & Physical Exam	X				X	X
Height & Weight	X					
ECOG Performance Status (see Appendix A)	X		X		X	X
Adverse Event Monitoring			X		X	X
SF-36 (QOL)	X		X		X	
LABORATORY-Serum						
Complete Blood Count with Differential	X	X 	X		X	X
Beta-HCG 	X					
Chemistry including: BUN, creatinine, glucose, sodium, potassium, chloride, bicarb, cholesterol, CK, calcium, total protein, LDH, magnesium, phosphorous, triglycerides, uric acid, TSH, amylase	X		X		X	X
BUN / Serum Creatinine	X		X		X	X
Hepatic Function Testing: ALT/AST, Bilirubin, Albumin, Alkaline Phosphatase	X	X 	X		X	X
β-2 Microglobulin / C-reactive protein	X		X		X	
Cardiac enzymes: BNP/ Troponin I	X		X		X	
Serum free light chain assay	X		X		X	
SPEP, SIFE, Immunoglobulins	X		X		X	
Vitamin B12, folate, ESR, retic %	X		X			
Coagulation profile: PTT, INR, D-dimer, Factor X	X		X		X	
Hepatitis Serologies: Hep B Surface Antigen, Hep B Core antibody, Hep C Antibody	X					
HIV antibody- 1+2	X					
CMV PCR	X			X		
1, 3 β-D-glucan	X			X		
LABORATORY-Urine						
Urinalysis	X				X	
24 hour urine: total protein, creatinine, kappa, and lambda	X				Every 6 months	
UPEP / UIFE / TV	X				X	
PATHOLOGY						
BM biopsy w/ MYD88 and CXCR4 WHIM analysis 	X					
FISH for t(11;14)	X					
Fat aspirate (if not previously done)	X					
X-RAYS AND SCANS						
ECG / CXR	X					
Echocardiogram	X				Every 6 months	
PFTs	X					

For women of childbearing potential only: Serum pregnancy test is required at screening.If bone marrow biopsy and aspiration must have been repeated following any previous therapy > 1 cycle.These visits including physical exam and blood work may be performed by local physician and confirmed by telephone contact if patient unable to return for week 2 visit or monthly visits on months 1 and 2.CBC with differential should be monitored every 2 weeks for the first 6 months of treatmentHepatic function tests should be checked every 2 weeks for the first 3 months of treatmentWhile on study drug or until disease progression or start of another therapy.30 days following last dose (+/-) 7 days.

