## OBJECTIVES

### 1.1.1 Title: Idelalisib for IgM-Associated AL Amyloidosis

### 1.1.2 Study Design:

This is a single arm, open label study designed to evaluate the safety and efficacy of idelalisib in patients with relapsed IgM-associated AL amyloidosis. Treatment will be comprised of idelalisib at 100mg orally twice daily, with permitted dose modifications for toxicity per manufacturer guidelines (Section 5). The medication will be continued until progression or significant toxicity.

After giving written informed consent, subjects will be evaluated for eligibility for enrollment in the study. Baseline evaluations will be performed as outlined in Section 7. Subjects who satisfy all inclusion and exclusion criteria will begin the study drug. Subjects will be monitored every cycle for safety and hematologic status. Organ function will also be measured during therapy.

Participants will be eligible to continue therapy as long as they do not demonstrate progressive disease or unacceptable toxicity. Standard response criteria for AL amyloidosis hematologic and organ response will be used (Gertz et al. 2010). Hematologic response will also be categorized and reported by Waldenstrom's macroglobulinemia hematologic response criteria. For the purposes of defining progressive disease, the amyloid response criteria will be used. Overall response rate will be measured and participants will be categorized into complete response, very good partial response, partial response and progressive disease. Progression free survival, organ response, safety and tolerability of idelalisib, and quality of life will be assessed.

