#### 4.1.4 Duration of Participation

Participants will continue to take Idelalisib per-protocol until disease progression or unacceptable adverse event. Study visits will occur two weeks after starting Idelalisib, then monthly from the start of Idelalisib for three months, followed by every three months from the start of Idelalisib thereafter until disease progression or the start of another line of therapy, whichever occurs first. For patients who have responded but come off Idelalisib for reasons other than progression, they will be followed every 6 months until progression or another line of therapy. An end of study visit will take place 30 days following the last dose of Idelalisib. The duration for individuals, and duration of the study, are dependent upon disease response. We anticipate no more than 2 years duration for individual subjects. We anticipate the study will remain active for a total of 4 years including enrollment, treatment, follow-up and data analysis.

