### 5. EXPECTED TOXICITIES AND DOSING DELAYS/DOSE MODIFICATIONS

If possible, symptoms should be managed symptomatically. In the case of toxicity, appropriate medical treatment should be used (including anti-emetics, anti-diarrheals, etc.). All adverse events experienced by participants will be collected from the time of the first dose of study treatment, through the study and until the final study visit. Participants continuing to experience toxicity at the off study visit may be contacted for additional assessments until the toxicity has resolved or is deemed irreversible.

For patients who are unable to tolerate the protocol-specified dosing schedule, dose adjustments are permitted. If administration of idelalisib must be interrupted because of unacceptable toxicity, drug dosing will be interrupted or modified according to the manufacturer's guidelines seen below. Toxicities requiring dose modification that recur upon restarting drug should be discussed with the principal investigator.

Dose Modifications for Toxicities Due to Idelalisib			
Pneumonitis: Discontinue Idelalisib in patients with any severity of symptomatic pneumonitis			
Intestinal Perforation: Discontinue Idelalisib			
Positive CMV PCR: Consider confirmation (at investigator discretion) Discontinue Idelalisib			
ALT/AST	>3-5 x ULN	>5-10 x ULN	>10 x ULN
	Maintain Idelalisib dose. Monitor at least weekly until <1 x ULN.	Withhold Idelalisib. Monitor at least weekly until ALT/AST are <1 x ULN, then may resume Idelalisib at 100 mg BID (or if taking 150mg BID, decrease to 100mg).	Discontinue Idelalisib permanently.

Bilirubin	>1.5-3 x ULN	>3-10 x ULN	>10 x ULN
	Maintain Idelalisib dose. Monitor at least weekly until <1 x ULN.	Withhold Idelalisib. Monitor at least weekly until bilirubin is <1 x ULN, then may resume Idelalisib at 100 mg BID (or if taking 150mg BID, decrease to 100mg).	Discontinue Idelalisib permanently.
Diarrhea	Moderate diarrhea (increase of 4-6 stools/day over baseline)	Severe diarrhea or Hospitalization (increase of 7 or more stools/day over baseline)	Life-threatening diarrhea
	Maintain Idelalisib dose. Monitor at least weekly until resolved.	Withhold Idelalisib. Monitor at least weekly until resolved, then may resume Idelalisib at 100 mg BID (or if taking 150mg BID, decrease to 100mg).	Discontinue Idelalisib permanently.

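### After month 3 the calendar schedules adverse-event checks only every three months, although the design section promises safety monitoring every cycle (about monthly)

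*Combined protocol and SAP*

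**What the plan says.** Section 1.1.2 (Study Design) states: "Subjects will be monitored every cycle for safety and hematologic status". This point concerns the safety half of that sentence.

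Section 4.1.4 sets visits at week 2 and months 1, 2 and 3, "followed by every three months from the start of Idelalisib thereafter". Section 6.1.4 ties dispensing to cycles: "For visits occurring monthly, one cycle worth of pills will be dispensed", and three cycles' worth at a three-monthly visit. Section 6.1.3 speaks of three-monthly visits and a three-month supply.

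In the Section 7.0 calendar, the adverse-event row is marked in the column for months 1 and 2, the three-monthly column and the end-of-treatment column. It is not marked in the column headed "Monthly while taking Idelalisib". The only rows marked there are CMV PCR and 1,3 β-D-glucan, and neither is marked in the three-monthly column.

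Footnote 3 allows the examination and blood work to be done by a local physician, confirmed by telephone, "if patient unable to return for week 2 visit or monthly visits on months 1 and 2". Footnote 4 says "CBC with differential should be monitored every 2 weeks for the first 6 months of treatment". Footnote 5 ends the two-weekly hepatic tests at month 3.

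Section 10.2 says that toxicity assessment follows the Section 7 calendar. For a positive CMV PCR, Section 5 says "Consider confirmation (at investigator discretion) Discontinue Idelalisib".

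**The concern.** The design section and the calendar give different intensities of safety follow-up after month 3. Because Section 10.2 points to the calendar, a site that follows the plan as written would not deliver what Section 1.1.2 states.

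Safety and tolerability is a secondary endpoint (Section 12.1). Section 2.1.5 reports excess deaths in other idelalisib trials, generally from infection, and names PJP and CMV among the infections. A patient between three-monthly visits may hold up to three cycles of tablets, with no scheduled enquiry about symptoms.

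The plan already requires a blood draw in each of those months, so a natural occasion for the enquiry exists. However, no safety contact is attached to it, and no provision says where it may be done.

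**Working it through.** The plan gives no figure of its own on this point, so the check is a count from the schedule.

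**1. Length of a cycle.** No section defines it. Two places agree on about one month:
- Section 6.1.4: one cycle of tablets at a monthly visit, three at a three-monthly visit.
- Section 10.2 sets organ assessment every six cycles, and the calendar sets the echocardiogram and 24-hour urine every six months.

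**2. Scheduled adverse-event checks on treatment.** From the calendar row and Section 4.1.4, these fall at months 1, 2, 3, 6, 9, 12, 15, 18, 21 and 24. The horizon of 24 months is the longest individual duration anticipated in Section 4.1.4.
- To month 12: 6 checks in 12 cycles.
- To month 24: 10 checks in 24 cycles.
- Cycles with no scheduled check: 12 − 6 = 6 and 24 − 10 = 14.

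**3. Monthly CMV PCR and β-D-glucan draws.** For each month on drug, is there a visit, or failing that another scheduled draw?

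| Months | Draws due | No visit | No visit and no other scheduled draw |
|---|---|---|---|
| 1–3 | 3 | 0 | 0 |
| 4–6 | 3 | 2 (months 4, 5) | 0 (two-weekly CBC still running) |
| 7–12 | 6 | 4 (months 7, 8, 10, 11) | 4 |
| 7–24 | 18 | 12 | 12 |

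From month 7 the share is 4/6 = 12/18 = two thirds. None of these months falls within the wording of footnote 3.

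**4. Work added by a monthly contact.** There are 14 months without a visit up to month 24 (4, 5, 7, 8, and so on to 23).
- All 18 patients on drug for 24 months: 14 × 18 = 252 calls.
- With drop-off, assume an exponential stay S(t) = 2^(−t/m), where m is the median in months. Calls = 18 × the sum of S(t) over the 14 months.
- m = 11 (the median PFS of the indolent NHL study in Section 2.1.8, used as a stand-in for time on drug): 18 × 6.419 = 115.5, or about 116.
- m = 3.6 (the median exposure in study 101-10, Section 2.1.6): 18 × 1.892 = 34.0.

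The documents do not give time on drug for this population. The medians and the exponential shape are assumptions, and 34 to 252 is the range they produce.

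**The case against.** The strongest case on the other side has four parts.

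- **Collection is continuous.** Section 5 collects adverse events from the first dose through the study. Section 9.2 records anything observed or reported by the subject. Section 9.3 requires events through 30 days after the last intervention to be followed, with dated records of those of Grade 2 or higher. This stands: the figure of 10 in 24 counts scheduled checks, not periods covered. It does not supply a scheduled enquiry between visits.
- **The conflict may be loose drafting.** Section 1.1.2 is an overview, the cycle is not defined, and monthly CMV PCR and β-D-glucan are themselves safety monitoring. This stands in part. Two laboratory tests do not cover the range of toxicities that the adverse-event row is there to find.
- **Draws without a visit are normal in this protocol.** The two-weekly CBC runs through months 4 and 5, and Section 5 asks for at least weekly tests after several toxicities, with no visit attached. Laboratory-only draws are nowhere forbidden. This stands: silence on where the samples are taken is missing detail, not an error.
- **Results are reviewed.** Section 9.2 requires abnormal results to be appraised, and Section 10.2 provides for weekly review of laboratory reports. This also stands.

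A reader might infer more: that CMV testing drops to every three months after month 6, so that infection is found late and patients stay on a drug they should have stopped. The documents do not support that. CMV PCR has one schedule, monthly, and a stop rule in Section 5. Any calculated delay would have to assume that staff depart from an explicit calendar row. Likewise, the absence of a Section 5 row for β-D-glucan does not show that positive results go unhandled, since the general appraisal rule applies and PJP prophylaxis is mandatory under Section 4.1.2.

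**Conclusion.** The point holds as a minor inconsistency that is cheap to correct. After month 3 the operative calendar schedules adverse-event checks every three months, against a stated intention of every cycle: 6 of the first 12 cycles and 10 of the first 24. This rests on a cycle of about one month, which the documents imply but do not define.

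The consequence is weaker scheduled ascertainment for a secondary endpoint, on a drug with a known risk of fatal infection. It is not a loss of all adverse-event data. No CMV or β-D-glucan test is missing, and no delay in detection follows if the calendar is followed. The two-thirds figure describes how many of these draws from month 7 lack a visit or another scheduled draw to go with them. How many samples or calls that amounts to depends on an assumed time on drug. The response-rate test and its power are unaffected.

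**What to change.** Make two changes to the Section 7.0 calendar in one amendment:

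1. Mark the adverse-event monitoring row in the monthly column, with a note that the check is done by telephone in months without a study visit.
2. Extend footnote 3 to the monthly column, so that CMV PCR and β-D-glucan may be drawn locally in those months, with telephone confirmation. The same call can then serve both purposes.

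No scheduled test or site visit is added. The cost is one short call per patient in each month without a visit: at most 252 in total, about 116 with an assumed 11-month median stay, and fewer if patients stop sooner. No new β-D-glucan action rule or fixed time limit for telephoning results is needed to resolve this point.

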### 2.1.6. Summary of Safety Data from Monotherapy Trials

On studies 101-02 (parent) and 101-99 (extension), no DLT was observed during the dose-escalation phase at doses of 50, 100, 200 and 350 mg PO BID, respectively. Therefore, an MTD was not reached. PK data showed no exposure differences between the cohort of patients who received 200 mg PO BID and 350 mg PO BID. Grade 3 or higher LFT elevations that occurred in 28 patients were transient and reversible, and not dose limiting, as they did not recur in 9 of the 14 (64%) patients who were re-challenged with idelalisib. During the 48-week study, the most frequent AEs of any grade were fatigue, diarrhea, pyrexia, nausea, rash, AST increase, cough and ALT increase. SAEs occurred in 44% of patients; the most frequent were pneumonia, febrile neutropenia, diarrhea, pulmonary embolism and acute renal failure. A total of 23 patients (12%) discontinued treatment due to AEs; the most frequent AEs were AST elevation and pneumonia. Twenty subjects (11%) died; 5 due to disease progression, 3 subjects from pneumonia and 12 attributed to fungal pneumonia, PJP, fungal sinusitis, acute respiratory distress, hypoxic respiratory failure, multi-organ failure, cardiac arrest, infection with neutropenia, septic shock and refractory MM. AEs leading to death were reported in 9/20 subjects. Of these, 3 were assessed as possibly related to idelalisib: pneumonia, fungal pneumonia and PJP.

On study 101-09 (indolent NHL), out of 125 participants, 108 and 86 subjects have been exposed to idelalisib 150 mg PO BID for >2 months and >4 months, respectively. Thirty seven percent had reductions to 100 mg PO BID or 75 mg PO BID during the study. Of 125 subjects, 123 (98%) reported an AE. The most frequent were diarrhea, fatigue, cough, neutropenia, nausea and pyrexia. Eighty-three subjects (66%) reported grade 3 or higher AE. The most frequent were neutropenia, diarrhea, increased ALT, pneumonia and increased AST. Twenty-two deaths (18%) were reported; 7 subjects (6%) experienced AES leading to death. AEs leading to death were ARDS, cardiomyopathy with cardiac

arrest, hypoxic respiratory failure and multi-organ failure, pneumonia, septic shock, toxoplasmosis and splenic infarction. Fifty-four patients (43%) experienced SAEs: diarrhea, pyrexia and pneumonia. A total of 19 patients (15%) discontinued the study due to AEs. Diarrhea, ALT and AST elevation, colitis and pneumonitis were the most frequently reported.

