### **4.1.1 Agent Administration**

#### **4.1.1 Idelalisib**

Idelalisib will be administered orally at a dose of 100 mg (one tablet) twice daily. At 3 month visit, if the patient has no toxicities grade 2 or greater that are attributable to idelalisib, dose escalation to 150 mg PO BID is allowed at investigator discretion. Participants will be treated until progression, unacceptable toxicity, or decision to withdraw from the trial. Dose reductions due to toxicity will be permitted, according to dose modification instructions (Section 5).

The study drug idelalisib will be self-administered, and participants will be instructed to write in a diary daily, documenting that the drug was taken. Participants will be instructed to take the study drug at approximately the same time each day. If a dose is missed, it can be taken up to 6 hours after the scheduled time with a return to the normal schedule the following day. If it has been greater than 6 hours, the dose should not be taken and the patient should take the next dose at the scheduled time the next day. The missed dose will not be made up and must be returned to the site at the next scheduled visit; this must be documented in the study diary. Furthermore, they will be instructed to call the PI or research nurse if vomiting occurs. If the pills are vomited a replacement dose should not be taken that day. All dosages prescribed and dispensed to the participant, and all dose changes during the study must be recorded.

Drug accountability will be done at each study visit; unused drug and diaries will be collected from the participant, unused drug will be counted and returned to the pharmacy to be destroyed. A new prescription for either one cycle or three cycles, will be filled by the participant.

Medication labels will comply with US legal requirements and be printed in English. The storage conditions for study drug will be described on the medication label.

Idelalisib will be provided by Gilead Sciences, Inc. Idelalisib is formulated as tablets for oral administration and will be available for this study in 150-mg tablets or 100-mg tablets.

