### 10.2 Data Monitoring Committee

Toxicity and accrual monitoring will be performed on a routine basis by the study investigators as well as the multidisciplinary members of the Amyloid Center at Boston University, which has over 40 years' experience in the treatment of AL amyloidosis. Subjects will undergo toxicity assessment, performance status assessment and laboratory tests according to the study calendar in Section 7. Organ response assessment will be conducted every six cycles. The clinical status and laboratory reports of the study participants will be reviewed routinely by the co-investigators at the weekly meetings of the Amyloid Program. Dose modifications/interruptions or discontinuation will be implemented according to Section 5.

In addition, the BMC Cancer Center's Internal Data and Safety Monitoring Committee (DSMC) will review the protocol, and will determine review frequency based on level of risk. The protocol will be reviewed at least annually by the DSMC. Please see full DSMB Charter in Appendix B.

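### Two-weekly liver tests stop at month 3, the visit at which escalation to 150 mg BID is allowed, so the next scheduled liver panel at the higher dose is about three months later

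*Combined protocol and SAP*

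**What the plan says.** **Liver tests.** Footnote 5 of the Section 7.0 calendar reads "Hepatic function tests should be checked every 2 weeks for the first 3 months of treatment". The hepatic row is also marked at enrollment, at months 1 and 2, at the three-monthly visits and at the end-of-treatment visit. It is blank in the monthly column. The separate chemistry row lists no ALT, AST or bilirubin.

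**Blood counts.** Footnote 4 reads "CBC with differential should be monitored every 2 weeks for the first 6 months of treatment", so these draws continue past month 3.

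**Dose.** Section 4.1.1 starts patients at 100 mg BID. At the 3 month visit, for a patient with no attributable toxicity of grade 2 or worse, "dose escalation to 150 mg PO BID is allowed at investigator discretion".

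**Visits.** Section 4.1.4 sets a visit at two weeks and monthly visits for three months, "followed by every three months from the start of Idelalisib thereafter until disease progression" or a new line of therapy.

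**General monitoring statements.** Section 1.1.2 says "Subjects will be monitored every cycle for safety and hematologic status". Section 10.2 says "Subjects will undergo toxicity assessment, performance status assessment and laboratory tests according to the study calendar in Section 7".

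**Liver dose rules.** Section 5 foresees a liver event at the higher dose. After a hold, once values recover, the site "then may resume Idelalisib at 100 mg BID (or if taking 150mg BID, decrease to 100mg".

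**The concern.** Close liver surveillance ends at the visit where the dose may rise by half. The month 3 panel is drawn before any exposure to 150 mg, so it says nothing about the new dose.

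The protocol's own background gives reason to watch liver enzymes at 150 mg BID. For grade 3 or higher events in study 101-09, which used that dose, Section 2.1.6 says "The most frequent were neutropenia, diarrhea, increased ALT, pneumonia and increased AST". It also lists ALT and AST elevation among the most frequent events leading to discontinuation there. Those patients started at 150 mg, so when a rise would appear after a step up from 100 mg is unknown.

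At stake is patient safety and, with it, the secondary endpoint of safety and tolerability. A symptomless rise at 150 mg could go unmeasured, with dosing continued, until month 6.

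**Working it through.** The plan states no figure for this interval, so there is none to reproduce. The check is whether any provision fills the gap, and then how long the gap is.

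**1. Does anything else schedule a liver panel between months 3 and 6?**

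- The two-weekly column is headed 3-6 months, but footnotes 4 and 5 divide it: blood counts to month 6, liver tests to month 3.
- The monthly column carries only CMV PCR and 1,3 β-D-glucan.
- The Section 1.1.2 statement names no liver test, and Section 10.2 refers laboratory tests back to the calendar.
- Weekly testing under Section 5 begins only after a measured ALT/AST >3 x ULN or bilirubin >1.5 x ULN.
- Section 6.1.4 dispenses three cycles of tablets at three-monthly visits, so resupply does not bring the patient back sooner.

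Nothing fills it.

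**2. Length of the gap (month 3 to month 6)**

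| Basis | Days |
|---|---|
| Three 28-day cycles (assumed; cycle length is not defined) | 3 x 28 = 84 |
| Three 60-tablet bottles at two tablets a day (Section 6.1.2) | 3 x 60/2 = 90 |
| Three calendar months | 89 to 92 |

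The range is 84 to 92 days, or about 12 to 13 weeks. Section 4.1.4 schedules by months, so 89 to 92 is the more natural reading.

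**3. Panels**

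- First three months at 100 mg: weeks 2, 4, 6, 8, 10 and 12, so 6 two-weekly panels.
- Between the month 3 and month 6 visits: 0 scheduled. A two-weekly schedule would give weeks 14 to 22 (5 panels) with the 84-day gap, or weeks 14 to 24 (6 panels) with the 92-day gap.

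**4. Patients affected.** The documents give no escalation rate for this trial. As an illustration only, Section 2.1.6 reports 28% dose-escalated in study 101-11, a different disease with escalation rules not given: 0.28 x 18 = 5.04, about 5 patients. The ceiling is all 18.

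**5. Effect on detection, under assumptions not in the documents.** Suppose onset is uniform over a gap of W = 12 to 13 weeks.

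- A rise lasting d weeks is seen at month 6 with probability d/W. For d = 2: 2/13 = 15% to 2/12 = 17%. For d = 4: 4/13 = 31% to 4/12 = 33%. For d = 6: 6/13 = 46% to 6/12 = 50%. Two-weekly panels see every rise with d ≥ 2. In this model the missed rises resolve on their own.
- A rise that persists is found at month 6, after a mean delay of W/2 = 6 to 6.5 weeks. With two-weekly panels the mean delay is 2/2 = 1 week.

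The second result matters more clinically, because the drug continues at 150 mg throughout the delay.

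**The case against.** The strongest reply concerns weight. No section shows excess liver toxicity after escalation or late in treatment. Escalation requires about three months on drug without attributable grade 2 or greater toxicity, after two-weekly liver panels and an entry limit on ALT/AST (exclusion 3.2.4). That screens out patients with early liver toxicity and weakens the comparison with 101-09.

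Other background is reassuring. Section 2.1.5 places severe hepatotoxicity mainly in younger front-line patients, with median onset at 28 days, and exclusion 3.2.14 keeps untreated patients out. Section 2.1.6 reports no dose-limiting toxicity from 50 to 350 mg BID in 101-02/101-99 and describes grade 3 or higher liver elevations there as transient and reversible. Section 2.1.7 reports less than dose-proportional pharmacokinetics, so the exposure rise should be below 150/100 = 1.5-fold. Concentrating liver tests early may have been deliberate, since the 28-day median supports it.

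Much of this stands and limits the weight. It does not close the gap. The onset figure counts from first dose, not from escalation. Elevations did not recur in 9 of 14 rechallenged patients, which leaves 5 of 14 (36%) outside that reassurance, and AST elevation was among the most frequent reasons for discontinuation in the same studies. The protocol gives no reason for ending liver tests at the escalation visit.

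It is also fair that the detection figures rest on assumed duration and onset, and that uniform onset sits poorly with a 28-day median. They show direction only.

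**Conclusion.** The concern holds. An escalated patient has no scheduled liver panel between the month 3 and month 6 visits, a gap of 89 to 92 days by calendar months, or 84 days if cycles are 28 days.

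Confidence is high for the gap and much lower for how often harm would follow, because the documents give neither an escalation rate nor the liver risk after a step up. The weight is minor to moderate: liver values only, in the escalated subset of at most 18 patients, with unscheduled tests still permitted. The change should be made because it closes a safety gap at very little cost.

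**What to change.** Add one sentence to footnote 5 of the Section 7.0 calendar:

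*After escalation to 150 mg BID, hepatic function tests are repeated every 2 weeks for a further 3 months, drawn with the two-weekly CBC (footnote 4).*

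The first panel at the new dose would then come 14 days after escalation. No other change is needed, because escalation is specified only at the 3 month visit and the blood-count draws already run to month 6.

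**Cost.** 5 to 6 added panels per escalated patient on blood already being drawn. With about 5 escalated patients that is 5 x 5 = 25 to 5 x 6 = 30 panels; if all 18 escalate, at most 18 x 6 = 108.

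**Trade-off.** Some rises that would have settled unnoticed will trigger weekly testing (ALT/AST >3 x ULN or bilirubin >1.5 x ULN) or a hold (ALT/AST >5 x ULN or bilirubin >3 x ULN) under Section 5.
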